12.4 Data monitoring committee

Data monitoring committee will not be used. An Independent Adjudication Committee will be used for adjudication of cardiovascular adverse events, see Section 12.4.1.

12.4.1 Independent Adjudication Committee

An Independent Adjudication Committee, blinded to the treatment of the patient, will classify cardiovascular AEs, such as, but not limited to, myocardial infarction and stroke reported in the study. A separate Adjudication Manual will define and describe the procedure for the handling, reporting and classification of these events.

13. IMPORTANT MEDICAL PROCEDURES TO BE FOLLOWED BY THE INVESTIGATOR

13.1 Medical emergencies and AstraZeneca/Bristol-Myers Squibb contacts

The Principal investigator is responsible for ensuring that procedures and expertise are available to handle medical emergencies during the study. A medical emergency usually constitutes a SAE and is to be reported as such, see Section 6.4.4.

In the case of a medical emergency the investigator may contact the Study Delivery Team Leader. If the Study Delivery Team Leader is not available, contact the Study Delivery Team Physician/other physician at the AstraZeneca Research and Development.

Reporting of unsolicited SAE 30 days after end of study treatment, see Section 6.4.3.9.

Name	Role in the study	Address & telephone number

13.2 Overdose

For the purposes of this study, before the randomisation code is broken, an overdose (of active or placebo) is defined as a dose exceeding 8 tablets for each day. After code break, an overdose is defined as a dose exceeding 40 mg of saxagliptin per day. Should an overdose (accidental or deliberate) occur, it must be reported in accordance with the procedures described below, regardless of whether the overdose was associated with any symptom or not. All symptoms associated with the overdose should be reported as AEs.

- An overdose with associated AEs is recorded as the AE diagnosis/symptoms on the relevant AE modules in the eCRF and on the Overdose eCRF module.
- An overdose without associated symptoms is only reported on the Overdose eCRF module.

For overdoses associated with SAE, standard reporting timelines apply, see Section 6.4.4. For other overdoses, reporting should be done within 30 days. An Overdose form will be used if WBDC system is not available.

Appendix B Additional Safety Information

FURTHER GUIDANCE ON THE DEFINITION OF A SERIOUS ADVERSE EVENT (SAE)

Life threatening

'Life-threatening' means that the subject was at immediate risk of death from the AE as it occurred or it is suspected that use or continued use of the product would result in the subject's death. 'Life-threatening' does not mean that had an AE occurred in a more severe form it might have caused death (eg, hepatitis that resolved without hepatic failure).

Hospitalisation

Out-patient treatment in an emergency room is not in itself a serious AE, although the reasons for it may be (eg, bronchospasm, laryngeal oedema). Hospital admissions and/or surgical operations planned before or during a study are not considered AEs if the illness or disease existed before the subject was enrolled in the study, provided that it did not deteriorate in an unexpected way during the study.

Important medical event or medical intervention

Medical and scientific judgement should be exercised in deciding whether a case is serious in situations where important medical events may not be immediately life-threatening or result in death, hospitalisation, disability or incapacity but may jeopardize the subject or may require medical intervention to prevent one or more outcomes listed in the definition of serious. These should usually be considered as serious.

Simply stopping the suspect drug does not mean that it is an important medical event; medical judgement must be used.

Examples of such events are:

- Angioedema not severe enough to require intubation but requiring iv hydrocortisone treatment
- Hepatotoxicity caused by paracetamol (acetaminophen) overdose requiring treatment with N-acetylcysteine
- Intensive treatment in an emergency room or at home for allergic bronchospasm
- Blood dyscrasias (eg, neutropenia or anaemia requiring blood transfusion, etc) or convulsions that do not result in hospitalisation
- Development of drug dependency or drug abuse.
- A guide to interpreting the causality QUESTION

The following factors should be considered when deciding if there is a "reasonable possibility" that an AE may have been caused by the drug.

- Time Course. Exposure to suspect drug. Has the subject actually received the suspect drug? Did the AE occur in a reasonable temporal relationship to the administration of the suspect drug?
- Consistency with known drug profile. Was the AE consistent with the previous knowledge of the suspect drug (pharmacology and toxicology) or drugs of the same pharmacological class? OR could the AE be anticipated from its pharmacological properties?
- Dechallenge experience. Did the AE resolve or improve on stopping or reducing the dose of the suspect drug?
- No alternative cause. The AE cannot be reasonably explained by another aetiology such as the underlying disease, other drugs, other host or environmental factors.
- Rechallenge experience. Did the AE reoccur if the suspected drug was reintroduced after having been stopped? AstraZeneca would not normally recommend or support a rechallenge.
- Laboratory tests. A specific laboratory investigation (if performed) has confirmed the relationship?

A "reasonable possibility" could be considered to exist for an AE where one or more of these factors exist.

In contrast, there would not be a "reasonable possibility" of causality if none of the above criteria apply or where there is evidence of exposure and a reasonable time course but any dechallenge (if performed) is negative or ambiguous or there is another more likely cause of the AE.

In difficult cases, other factors could be considered such as:

- Is this a recognised feature of overdose of the drug?
- Is there a known mechanism?

Ambiguous cases should be considered as being a "reasonable possibility" of a causal relationship unless further evidence becomes available to refute this. Causal relationship in cases where the disease under study has deteriorated due to lack of effect should be classified as no reasonable possibility.

Clinical Study Protocol Appendix C				
Drug Substance	Saxagliptin			
Study Code	D1680L00002			
Edition Number	1			
Date				

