5.4.2 Methods for unblinding the study

Individual treatment codes, indicating the treatment randomisation for each randomised patient, will be available to the investigator(s) from the IWRS. Routines for this will be described in the IWRS user manual that will be provided to each study centre.

Patients in the study can be unblinded through the IWRS. This can be carried out in emergencies by the investigator(s) at the study centre and the personnel who are independent to the study evaluation at the Pharmacovigilance Department, Bristol-Myers Squibb. If a patient is admitted for an emergency to a clinic that is not participating in the study, AstraZeneca will have an external provider for an unblinding service, 24 hours per day, 7 days a week.

The treatment code should not be broken except in medical emergencies when the appropriate management of the patient requires knowledge of the randomised treatment. The investigator documents and reports the action to AstraZeneca, without revealing the treatment given to patient to the AstraZeneca study personnel. Patients, whose double-blind treatment codes are broken, should be discontinued from the study as soon as possible.

AstraZeneca and Bristol-Myers Squibb retains the right to break the code for SAEs that are unexpected and are suspected to be causally related to an investigational product and that potentially require expedited reporting to regulatory authorities.

Treatment codes will not be broken for the planned analyses of data until all decisions on the evaluability of the data from each individual patient have been made and documented.

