6.4.2 Definitions of serious adverse event

A serious adverse event (SAE) is an AE occurring during any study phase (ie, enrolment, lead-in, titration and maintenance treatment periods), that fulfils one or more of the following criteria:

- Results in death
- Is immediately life-threatening
- Requires in-patient hospitalisation or prolongation of existing hospitalisation
- Results in persistent or significant disability or incapacity
- Is a congenital abnormality or birth defect
- Is an important medical event that may jeopardise the patient or may require medical intervention to prevent one of the outcomes listed above
- Cancer
- Drug dependency/abuse

For further guidance on the definition of a SAE, see Appendix B.

SAEs related to bone fracture, skin lesions, infection, lymphocytopenia, thrombocytopenia and symptomatic hand and foot oedema should be given special attention. Regarding bone fractures is should include both non-serious and serious events. Supplemental paper CRF are to be completed by the study investigators for these specific AEs/SAEs.

For the purposes of regulatory reporting, the following events/medical conditions should be reported as described in Section 6.4.4, in the same timelines as SAEs regardless of whether the event/medical condition is classified as serious or non-serious:

- Pancreatitis
- Opportunistic infections (eg, tuberculosis, Herpes zoster, cytomegalovirus, Pneumocystis jirovecii, etc)

Serum AST or ALT greater than or equal to 3 times ULN concomitant with serum total bilirubin greater than 2 times ULN or evidence of jaundice.

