6.4.3.4 Causality collection

The investigator will assess causal relationship between investigational products and each AE, and answer "yes" or "no" to the question "Do you consider that there is a reasonable possibility that the event may have been caused by the investigational products?" If there is any valid reason, even if undetermined or untested, for suspecting a possible cause-and-effect relationship between the investigational products and the occurrence of the AE, then this should be answered "yes". Otherwise, if no valid reason exists for suggesting a possible relationship, then this should be answered "no". If more than one AE is identified, a causality assessment must be made for each AE.

For SAEs causal relationship will also be assessed for other medication and study procedures. Note that for SAEs that could be associated with any study procedure the causal relationship is implied as "yes".

A guide to the interpretation of the causality question is found in Appendix B.

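### For an event with fitting exposure and timing, Appendix B answers no to causality on an ambiguous dechallenge, against its own default and Section 6.4.3.4

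*Protocol*

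**What the plan says.** Four statements in the protocol bear on the investigator's causality answer.

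- **Section 6.4.3.4** sets the question and the threshold. The answer is yes "If there is any valid reason, even if undetermined or untested, for suspecting a possible cause-and-effect relationship" between product and event; otherwise it is no. The section then names Appendix B as the guide to interpretation.
- **Appendix B, general rule.** After six factors (time course, known drug profile, dechallenge, no alternative cause, rechallenge, laboratory tests), a reasonable possibility "could be considered to exist for an AE where one or more of these factors exist".
- **Appendix B, exclusion.** The next sentence opens as a contrast. It denies a reasonable possibility when no factor applies, when another cause is more likely, or "where there is evidence of exposure and a reasonable time course but any dechallenge (if performed) is negative or ambiguous".
- **Appendix B, default.** After some extra questions for difficult cases: "Ambiguous cases should be considered as being a" reasonable possibility, unless later evidence refutes it.

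Section 6.4.3.3 makes the answer a recorded variable for every adverse event. Section 5.4.2 lets the sponsors break the code for "SAEs that are unexpected and are suspected to be causally related to an investigational product" where expedited reporting may be needed. Section 6.4.4 requires every serious adverse event to be reported whatever its causality rating.

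**The concern.** An investigator who follows the section to its guide can reach opposite answers for the same event. Suppose the timing fits and the drug was stopped, but the course afterwards was unclear. The exclusion sentence gives no; the default for ambiguous cases and Section 6.4.3.4 give yes. The protocol does not say which instruction prevails, and about 175 centres will be applying them.

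Two uses of the answer are at stake. The recorded rating may not mean the same thing from site to site. A rating of no may also make it harder to recognise an unexpected suspected reaction as a candidate for the code break in Section 5.4.2.

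**Working it through.** No figure in the protocol depends on this wording, so there is none to reproduce. The check is a comparison of the texts, followed by a count of logical patterns.

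**Texts side by side**, for events where exposure and a reasonable time course are present:

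| Dechallenge | Exclusion sentence | Default for ambiguous cases | Section 6.4.3.4 | Result |
|---|---|---|---|---|
| Ambiguous | no | yes, until refuted | yes: the suspicion is undetermined | contradiction |
| Negative, another valid reason remains (for example drug profile or a confirming test) | no | does not speak to it | yes | conflict with Section 6.4.3.4 |
| Negative, timing alone supports causality | no | does not speak to it | no further reason for suspicion | no conflict shown |
| Positive or not done | not triggered | – | – | no conflict |

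The second row arises because the exclusion is not limited to events supported by timing alone.

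**How broad the exclusion is.** Inputs are the six Appendix B factors. Five are coded as two-valued: time course, drug profile, no alternative cause versus a more likely one, rechallenge, laboratory test. Dechallenge has four states: positive, negative, ambiguous, not done.

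1. All patterns: 2^5 × 4 = 128, so 128 / 4 = 32 for each dechallenge state.
2. The exclusion needs a fitting time course: 32 / 2 = 16 patterns for a negative dechallenge and 16 for an ambiguous one. It is never triggered in the other two states.
3. Time course is itself a listed factor, so all 16 of each 16 also meet the one-or-more rule.
4. Four two-valued factors remain: 2^4 = 16, of which one has no further support. So 16 − 1 = 15 of each 16 carry at least one further supporting factor, and the sentence read literally still gives no.
5. Some of these would be no anyway, because a more likely other cause is a separate ground for no. Removing that half leaves 16 / 2 = 8 of each 16 where the dechallenge wording is the only route to no. In all 8 the absence of an alternative cause is a further supporting factor.

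These counts show how widely the sentence is drawn. They are not frequencies and say nothing about how many events in the trial would be affected.

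**The case against.** **The exclusion is an exception, not a contradiction.** The one-or-more rule is permissive and the next sentence announces a contrast, so it can be read as carving out events supported only by timing. This stands against any claim that the two sentences flatly contradict each other. It does not remove the clash with the default for ambiguous cases or with Section 6.4.3.4, and the appendix does not state the limit to timing alone.

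**The default concerns the whole case, not the dechallenge.** It closes a paragraph on difficult cases and works as a tie-break, so an event with an unclear dechallenge would end at yes. That is a sensible reading, but the exclusion sentence still says no for the same event and nothing ranks the two.

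**Section 6.4.3.4 controls and Appendix B only guides.** This is probably what was meant, and it supports the fix. The protocol does not say so.

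**Serious reactions are not lost.** A reader might infer that they could go unreported. The protocol does not support that: Section 6.4.4 makes reporting independent of causality, and Section 5.4.2 does not make the investigator's answer the only source of suspicion. Other review also exists. A sponsor medical expert reviews events not reported as serious or as leading to discontinuation (Section 11.2.2), and a blinded committee classifies cardiovascular events (Section 12.4.1), although no causality role is stated for it.

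**Events that do not resolve on stopping.** A reader might also infer that fracture, infarction, stroke or cancer would be pushed to no by their nature. Nothing in the protocol classes stopping drug after an irreversible event as a negative dechallenge, and the exclusion applies only where a dechallenge was performed. Section 6.4.2 does say "SAEs related to bone fracture, skin lesions, infection, lymphocytopenia, thrombocytopenia and symptomatic hand and foot oedema should be given special attention", but it asks for supplementary forms on these events without a causality condition.

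**Conclusion.** The point holds in a limited form. For an event with fitting exposure and time course and an ambiguous dechallenge, Appendix B contradicts itself and Section 6.4.3.4. For a clearly negative dechallenge there is a conflict, with Section 6.4.3.4 only, where another valid reason for suspicion remains.

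The consequence is an inconsistent investigator causality rating, with a possible effect on recognising unexpected suspected reactions. Its size cannot be derived: the protocol gives no rate of serious events and no share with a negative or ambiguous dechallenge, so any count would rest wholly on assumed rates. The conclusion depends on reading the sentences as written and on the absence of any rule of precedence. Weight is minor to moderate, with no effect on the primary endpoint, sample size or type I error.

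**What to change.** Reconcile the passages with two wording changes in Appendix B.

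1. Delete *or ambiguous* from the sentence that opens with the contrast, so that ambiguous dechallenges fall under the appendix's own default.
2. State that Section 6.4.3.4 prevails wherever the guide differs from it. The negative-dechallenge exclusion then applies only when no other valid reason for suspicion remains.

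No new criterion about which kinds of event should resolve on stopping is needed; that would be an additional causality rule and goes beyond reconciling the text.

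The cost is an edit to the appendix and a note to sites. The downside is a few more events rated related and possibly a few more expedited reports.

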Appendix C International Airline Transportation Association (IATA) 6.2 Guidance Document

LABELLING AND SHIPMENT OF BIOHAZARD SAMPLES

International Airline Transportation Association (IATA) classifies biohazardous agents into 3 categories (http://www.iata.org/whatwedo/cargo/dangerous_goods/infectious_substances. htm). For transport purposes the classification of infectious substances according to risk groups was removed from the Dangerous Goods Regulations (DGR) in the 46th edition (2005). Infectious substances are now classified either as Category A, Category B or Exempt. There is no direct relationship between Risk Groups and categories A and B.

Category A Infectious Substances are infectious substances in a form that, when exposure to it occurs, is capable of causing permanent disability, life-threatening or fatal disease in otherwise healthy humans or animals. Category A pathogens are eg, Ebola, Lassa fever virus:

• are to be packed and shipped in accordance with IATA Instruction 602.

Category B Infectious Substances are infectious Substances that do not meet the criteria for inclusion in Category A. Category B pathogens are eg, Hepatitis A, B, C, D, and E viruses, Human immunodeficiency virus (HIV) types 1 and 2. They are assigned the following UN number and proper shipping name:

- UN 3373 Biological Substance, Category B
- are to be packed in accordance with UN3373 and IATA 650

Exempt - all other materials with minimal risk of containing pathogens

- Clinical trial samples will fall into Category B or exempt under IATA regulations
- Clinical trial samples will routinely be packed and transported at ambient temperature in IATA 650 compliant packaging (http://www.iata.org/whatwedo/cargo/dangerous_goods/infectious_substances. htm)
- Biological samples transported in dry ice require additional dangerous goods specification for the dry-ice content
- IATA compliant courier and packaging materials should be used for packing and transportation and packing should be done by an IATA certified person, as applicable
- Samples routinely transported by road or rail are subject to local regulations which require that they are also packed and transported in a safe and appropriate way to contain any risk of infection or contamination by using approved couriers and packaging / containment materials at all times. The IATA 650 biological sample containment standards are encouraged wherever possible when road or rail transport is used.

Clinical Study Protocol Appendix DDrug SubstanceSaxagliptinStudy CodeD1680L00002Edition Number1Date

Appendix D Diabetes Treatment Statisfaction Questionnaire (DTSQs) and (DTSQc)
Diabetes Treatment Satisfaction Questionnaire: DTSQs

The following questions are concerned with the treatment for your diabetes (including insulin, tablets and/or diet) and your experience over the past few weeks. Please answer each question by circling a number on each of the scales.

1.	How satisfied are you with your current treatment?											
	very satisfied	6	5	4	3	2	1	0	very dissatisfied			
2.	How often have you felt that your blood sugars have been unacceptably high recently?											
	most of the time	6	5	4	3	2	1	0	none of the time			
3.	How often have you felt that your blood sugars have been unacceptably low recently?											
	most of the time	6	5	4	3	2	1	0	none of the time			
4.	How convenient have you been finding your treatment to be recently?											
	very convenient	6	5	4	3	2	1	0	very inconvenient			
5.	How flexible have you been finding your treatment to be recently?											
	very flexible	6	5	4	3	2	1	0	very inflexible			
6.	How satisfied are you with your understanding of your diabetes?											
	very satisfied	6	5	4	3	2	1	0	very dissatisfied			
7.	Would you recommend this form of treatment to someone else with your kind of diabetes?											
	Yes, I would definitely recommend the treatment	6	5	4	3	2	1	0	No, I would definitely not recommend the treatment			
8.	How satisfied would you be to continue with your present form of treatment?											
	very satisfied	6	5	4	3	2	1	0	very dissatisfied			
	Please make sure ti	hat yoı	u have	e circ	led on	ie nur	nber (on each) of the scales.			

Diabetes Treatment Satisfaction Questionnaire (change): DTSQc

For the past few weeks/months you have been taking part in a diabetes treatment study. At the start of the study you may have had a change of treatment. Today we would like to know how your experience of your current treatment (including medication and diet) has changed from your experience of treatment before the study began. Please answer each question by circling a number on each of the scales to indicate the extent to which you have experienced changes. If you have experienced no change, please circle '0'.

1.	How satisfied are you with your current treatment?											
	much more satisfied now	3	2	1	0	-1	-2	-3	much less satisfied now			
2.	How often have you felt that your blood sugars have been unacceptably high recently?											
	much more of the time now	3	2	1	0	-1	-2	-3	much less of the time now			
3.	How often have you felt that your blood sugars have been unacceptably low recently?											
	much more of the time now	3	2	1	0	-1	-2	-3	much less of the time now			
4.	How convenient have you been finding your treatment to be recently?											
	much more convenient now	3	2	1	0	-1	-2	-3	much less convenient now			
5.	How flexible have you been finding your treatment to be recently?											
	much more flexible now	3	2	1	0	-1	-2	-3	much less flexible now			
6.	How satisfied are you wi	th you	ur unde	rstand	ing of y	your dia	abetes	?				
	much more satisfied now	3	2	1	0	-1	-2	-3	much less satisfied now			
7.	How likely would you be to recommend your present treatment to someone else with your kind o diabetes?											
	much more likely to recommend the treatment now	3	2	1	0	-1	-2	-3	much less likely to recommend the treatment now			
8.	How satisfied would you be to continue with your present form of treatment?											
	much more satisfied now	3	2	1	0	-1	-2	-3	much less satisfied now			
	Please make su	re tha	t you l	have c	ircled	one ni	umber	on each	of the scales.			

Clinical Study Protocol Appendix E

Drug Substance Study Code Edition Number Date Saxagliptin D1680L00002 1

